14.3. Analysis Populations

Safety Population:

All subjects who were administered any test article.

Per-Protocol Population:

All subjects who have successfully completed all visits and did not substantially deviate from the protocol as determined by the trial cohort review committee prior to database hard lock (Per-Protocol Population). Justification of excluding subjects with protocol deviations will be documented in a memo to file.

Intention-to-Treat (ITT) Population:

Intention-to-treat population will include all assigned subjects.

14.4. Level of Statistical Significance

The Type I error rate of the trial will be controlled at 1-sided 0.025 level. Each co-primary safety and efficacy hypothesis will be tested using a 1-sided Type I error of 0.025. All co-primary hypotheses must be met to satisfy the study objectives and to test any secondary hypotheses.

Based on a gate keeping approach between the primary and secondary families of hypotheses, all primary endpoints must show statistical significance at one-sided 0.025 level in order to pass the full alpha level to test the secondary endpoints hypotheses.

A fixed sequence testing procedure will be utilized to test the secondary hypotheses to control the Type I error rate also in the secondary family of hypotheses. Each secondary hypotheses will be tested using a 1-sided 0.025 level following the order prespecified in section 2.3.3. Based on the fixed sequence principle, each secondary endpoint must be found statistically significant at a one-sided 0.025 level in order to proceed to the next step. If not, the testing procedure of the secondary endpoints will stop.

14.5. Primary Analysis

The co-primary efficacy analyses will be conducted on the ITT population, while co-primary safety analyses will be conducted on the safety population. All efficacy and safety analyses will be based on observed case data with no imputation of missing values.

14.5.1. Co-Primary Efficacy Analyses

Binocular HLHC Distance, Intermediate and, Near LogMAR Visual Acuity

Binocular, high luminance, high contrast visual acuity on logMAR scale after approximately 2-Weeks in the optimized lenses will be analyzed using a linear mixed model. Distance (distance/intermediate/near), sphere strata (hyperope and myope) and the interaction between distance by sphere strata will be included as fixed effects. Other baseline characteristics, such as age, gender and add power may be included as covariates when appropriate. Site will be

included as random effect (G-side). The covariance between residual errors from the same subject across distance will be modeled using an unstructured (UN) covariance structure. Mean estimates will be conducted using two-sided confidence intervals (CI) constructed for the least square mean. One-sided p-values will also be calculated.

The null and alternative hypothesis for binocular distance HLHC visual performance to test for superiority of the investigational lens relative to the pre-defined threshold of 0.00 logMAR is as follows:

 $\begin{array}{l} H_o: \mu_{Test} \geq 0.00 \; \mathrm{logMAR} \\ H_A: \mu_{Test} < 0.00 \; \mathrm{logMAR} \end{array} \end{array}$

Where μ_{Test} represents the population mean for the investigational lens after 2-weeks lens wear with respect to distance binocular HLHC VA. The investigational lens will be declared statistically significantly lower than 0.00 logMAR if the one-sided p-values is below 0.025.

The null and alternative hypothesis for binocular intermediate HLHC visual performance to test for superiority of the investigational lens relative to the pre-defined threshold of 0.17 logMAR is as follows:

 $\begin{array}{l} H_o: \mu_{Test} \geq 0.17 \; \mathrm{logMAR} \\ H_A: \mu_{Test} < 0.17 \; \mathrm{logMAR} \end{array} \end{array}$

Where μ_{Test} represents the population mean for the investigational lens after 2-Weeks lens wear with respect to intermediate binocular HLHC VA. The investigational lens will be declared statistically significantly lower than 0.17 logMAR if the one-sided p-values is below 0.025.

The null and alternative hypothesis for binocular near HLHC visual performance to test for superiority of the investigational lens relative to the pre-defined threshold of 0.17 logMAR is as follows:

 $\begin{array}{l} H_o: \mu_{Test} \geq 0.17 \; \mathrm{logMAR} \\ H_A: \mu_{Test} < 0.17 \; \mathrm{logMAR} \end{array} \end{array}$

Where μ_{Test} represents the population mean for the investigational lens after 2-weeks lens wear with respect to near binocular HLHC VA. The investigational lens will be declared statistically significantly lower than 0.17 logMAR if the one-sided p-values is below 0.025.

CLUE Vision Scores

CLUE Vision Scores after approximately 2-Weeks in the optimized lenses will be analyzed using a linear mixed model adjusting for baseline scores as a covariate. Strata (hyperope and myope) will be included as the only fixed effect. Other baseline characteristics known of importance such as age, gender and Additional (ADD) power may be included as covariates when appropriate. Site will be included as random effect (G-side). The Kenward and Roger method will be used for the calculation of the denominator of degrees of freedom¹⁵. Mean estimates will be conducted using two-sided confidence intervals (CI) constructed for the least square mean. One-sided p-values will also be calculated.

The null and alternative hypothesis to test for superiority of the myopic subjects relative to the pre-defined threshold of 41 for the investigational lens is as follows:

$$H_o: \mu_{Myopes} \le 41$$

$$H_A: \mu_{Myopes} > 41$$

Where μ_{Myopes} represents the population mean for the investigational lens after 2-Weeks lens wear with respect to CLUE Visions scores for myopic subjects. The investigational lens will be declared statistically significantly greater than 41 if the one-sided p-values is below 0.025.

The null and alternative hypothesis to test for superiority of the hyperopic subjects relative to the pre-defined threshold of 36 for the investigational lens is as follows:

$$H_o: \mu_{Hyperopes} \le 36$$

 $H_A: \mu_{Hyperopes} > 36$

Where $\mu_{Hyperopes}$ represents the population mean for the investigational lens after 2-weeks lens wear with respect to CLUE Visions scores for hyperopic subjects. The investigational lens will be declared statistically significantly greater than 36 if the one-sided p-values is below 0.025.

Toric Lens Orientation and Rotational Stability at least 15-minutes Following Settling

Absolute toric lens orientation (degrees) will be dichotomized as Y = 1 if absolute toric lens rotation (degrees) $\leq 10^{\circ}$) and Y = 0 otherwise. Rotational stability will be quantified by lens stability with blinks (degrees). Lens stability will be dichotomized as X = 1 if the lens stability with blinks (degrees) $\leq 5^{\circ}$ and X = 0 otherwise.

Absolute toric lens orientation and rotational stability will be analyzed separately using a Bayesian beta-binomial model with correlated binary data¹⁴.

The Model:

Let Y (the percentage of eyes with grade 3 or higher SLFs) be the sum of equicorrelated binary responses (Y_1 and Y_2 denotes left and right eyes, respectively) with probability of success p and correlation coefficient ρ .

The probability distribution of $Y = Y_1 + Y_2$ is obtained by the mixture of two variables. One of them follow a binomial distribution Bin(2, p) with probability of success p and mixing probability $(1 - \rho)$, and the other follows a modified Bernoulli distribution MBern(p), taking values 0 and 2, with probability of success p and mixing probability ρ :

$$P(Y = y | p, \rho) = (1 - \rho) Bin(2, p)I_{A1} + \rho MBern(p)I_{A2}$$

where $I_{A1} = \{0, 1, 2\}$, $I_{A2} = \{0, 2\}$ and *p* is the probability of success (i.e. proportion of eyes with Grade 3 or Higher SLFs).

To overcome the complexity of the mixture likelihood, a latent variable Z_i , i = 1, 2 is introduced in the model to indicate in which component of the correlated binary model the observation y_i , i = 1, 2 belongs to, that is,

$$Z_i = \begin{cases} 1 & \text{if the observation belong to } MBern(p) \\ 0 & \text{if the observation belong to } Bin(2,p) \end{cases}$$

The joint distribution of the augmented data (Y_i, Z_i) , i = 1, 2, is given by

$$\begin{split} P(Y = y_i, Z = z_i | p, \rho) \\ &= \rho^{z_i} \, p^{\frac{y_i z_i}{2}} \, (1-p)^{(2-y_i)\frac{z_i}{2}} \, (1-\rho)^{1-z_i} \, \begin{pmatrix} 2 \\ y_i \end{pmatrix} \, p^{y_i \, (1-z_i)} \, (1-p)^{(2-y_i)(1-z_i)} \end{split}$$

The probability p links to the regression variables through a logit transformation as follow: $logit(p) = \beta_o + \beta_1 lens$

It is assumed that β_o , β_1 and ρ to be independent with a non-informative prior N(0, 1000) for β_o and β_1 , and beta(0.5, 0.5) for ρ . The Metropolis sampler algorithm as implemented in the SAS/STAT MCMC procedure¹¹ will be used to estimate the posterior distributions of the parameters (β_o , β_1 , ρ). Inferences will be made based on a posterior credible interval for the relevant parameters.

The null and alternative hypotheses for evaluating superiority of the Test lens relative to 0.80 for are as follows:

$$H_o: p_T \le 80\%$$

 $H_1: p_T > 80\%$

JJVC CONFIDENTIAL

where p_T is the percentage of eyes with absolute toric rotation $\leq 10^\circ$ (or lens stability $\leq 5^\circ$) for the investigational lens. Based on Bayesian posterior probability distribution of the proportion p_T , superiority is interpreted as 95% probability of the investigational lens being statistically higher than the threshold of 80% (i.e., $p_T > 80\%$). If the lower bound of the 95% central posterior credible interval is above 80%, it will be concluded that there is 95% probability that the investigational lens is statistically significantly higher than 80% based on observed sample.

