14.2. Sample Size Justification

The total sample size of 140 subjects who complete the study (Visit 3) was calculated to provide adequate power in detecting statistical superiority of the Test lens relative to prespecified thresholds for binocular distance, intermediate and near logMAR VA, CLUE vision Scores, Absolute toric rotation, rotational stability, rate of unacceptable lens fitting and rate of grade 3 or higher SLFs. All co-primary effectiveness and safety hypotheses are required to achieve statistical significance for the study objective to be satisfied, therefore no adjustment for multiple primary hypotheses is necessary. Each co-primary hypothesis will be tested using a 1-sided Type I error rate of 0.025.

Thresholds for hypotheses associated with CLUE vision, comfort and, handling scores are from a meta-analysis of 14 JJVCI clinical trials of toric and multifocal toric contact lenses used by habitual contact lens wearers aged 40 to 70 years¹². In this analysis, baseline CLUE scores (for subjects' habitual contact lenses) from 14 clinical studies were analyzed to establish thresholds reflecting the "real-world" performance of contact lenses wearers in this population

JJVC CONFIDENTIAL

with respect to CLUE vision, comfort, and handling scores. Thresholds for all other endpoints were based on clinically relevant margins.

Additionally, this study was also powered to test superiority for secondary endpoints with respect to CLUE vision, comfort and, handling scores and lens fit success using a 1-sided Type I error rate of 0.025. Secondary endpoints will be tested using a fixed sequence approach. Further details on the preservation of the study overall Type I error rate are in Section 14.4.

The sample size of 140 to complete yields at least 81% overall power to detect statistical superiority for all co-primary endpoints. This sample size provides a statistical power of at least 99% for each co-primary and secondary endpoint. To account for subject drop-out approximately 155 subjects will be enrolled to ensure at least 140 subjects complete the study.

Endpoint Domain	Endpoint	Statistical Test Type (Statistically Significantly)	Sample Size	Power (%)
Primary Efficacy	Distance (4m) Binocular Visual Acuity (logMAR)	Superiority: mean VA< 0.00	9	99.1
	Intermediate (64cm) Binocular Visual Acuity (logMAR)	Superiority: mean VA< 0.17	6	99.5
	Near (40cm) Binocular Visual Acuity (logMAR)	Superiority: mean VA< 0.17	29	99.1

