ruore /.	instorical	Data	υ,	Lindpoint

SD: Standard Deviation

*Summaries for primary efficacy and secondary endpoints were provided for the per-protocol population at the 1-week follow-up evaluation.

**Summaries for the primary safety endpoints were provided for the safety population; all available data was included

Co-Primary Efficacy Endpoint Sample Size Calculations:

Distance, Intermediate and, Near logMAR Visual Acuity

Sample size calculations for distance, intermediate and near visual acuity were carried out separately using one-sided, one-sample mean t-test, with a one-sided Type I error rate of 0.025 for each hypothesis using the *One-Sample T-Tests for Superiority by a Margin* procedure in Power Analysis & Sample Size (PASS2021) software Version 21.0.6 (NCSS LLC, Kaysville UT)¹³. To preserve the overall study power, each endpoint was powered to approximately 99%. The assumptions for averages and standard deviations were made based on historical values from previous studies (Table 7).

CLUE Vision Scores (Hyperopes and Myopes)

Sample size calculations for CLUE Vision scores were carried out separately for each sphere stratum (hyperopes and Myopes) using one-sided, one-sample mean t-test, with a one-sided Type I error rate of 0.025 for each hypothesis using the *One-Sample T-Tests for Superiority by a Margin* procedure in Power Analysis & Sample Size (PASS2021) software Version 21.0.6 (NCSS LLC, Kaysville UT)¹³. To preserve the overall study power, each endpoint was powered to approximately 99%. The assumptions for averages and standard deviations were made based on historical values from previous studies (Table 7).

Toric Rotation and Lens Stability

The reference rate for absolute toric lens rotation $\leq 10^{\circ}$ was based on the historical results of 90.2%. The reference rate for lens stability $\leq 5^{\circ}$ was based on the worst-case scenario of 99%, given the historical results show 100%. Toric lens orientation and rotational stability, respectively, are defined as a binary response:

Toric Lens Orientation : Y
=
$$\begin{cases} 1 & \text{if a subject eye has absolute toric lens rotation} \leq 10^{\circ}, \\ 0 & \text{Otherwise} \end{cases}$$

Rotational stability: $Z = \begin{cases} 1 & \text{if a subject eye has lens stability with blinks } \leq 5^\circ, \\ 0 & \text{Otherwise} \end{cases}$

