14.6. Secondary Analyses

CLUE Vision, Comfort and, Handling

Secondary endpoints for CLUE vision, comfort and handling, scores after 2-weeks of lens wear will be analyzed separately using the same model as described above for primary analysis of CLUE vision scores.

The null and alternative hypothesis to test for superiority of the hyperopic subjects relative to the pre-defined threshold of 46 for the investigational lens is as follows:

 $H_o: \mu_{Hyperopes} \le 46$ $H_A: \mu_{Hyperopes} > 46$

Where $\mu_{Hyperopes}$ represents the population mean for the investigational lens after 2-weeks lens wear with respect to CLUE handling scores for hyperopic subjects. The Test lens will be declared statistically significantly greater than 46 if the one-sided p-values is below 0.025.

The null and alternative hypothesis to test for superiority of the hyperopic subjects relative to the pre-defined threshold of 38 for the investigational lens is as follows:

 $H_o: \mu_{Hyperopes} \le 38$ $H_A: \mu_{Hyperopes} > 38$

Where $\mu_{Hyperopes}$ represents the population mean for the investigational lens after 2-weeks lens wear with respect to CLUE comfort scores for hyperopic subjects. The Test lens will be declared statistically significantly greater than 38 if the one-sided p-values is below 0.025.

The null and alternative hypothesis to test for superiority of the myopic subjects relative to the pre-defined threshold of 55 for the investigational lens is as follows:

$$\begin{array}{l} H_o: \mu_{Myopes} \leq 55 \\ H_A: \mu_{Myopes} > 55 \end{array} \end{array}$$

Where μ_{Myopes} represents the population mean for the investigational lens after 2-weeks lens wear with respect to CLUE handling scores for myopic subjects. The investigational lens will be declared statistically significantly greater than 55 if the one-sided p-values is below 0.025.

The null and alternative hypothesis to test for superiority of the hyperopic subjects relative to the pre-defined threshold of 41 for the Test lens is as follows:

$$H_o: \mu_{Hyperopes} \le 41$$

 $H_A: \mu_{Hyperopes} > 41$

Where $\mu_{Hyperopes}$ represents the population mean for the investigational lens after 2-weeks lens wear with respect to CLUE vision scores for hyperopic subjects. The investigational lens will be declared statistically significantly greater than 41 if the one-sided p-values is below 0.025.

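### The CLUE threshold tests use a baseline-adjusted least-squares mean whose target and standard error do not match the stratum population mean in the hypothesis, so the one-sided 0.025 level is not assured

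*Combined protocol and SAP*

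**What the plan says.** Section 14.5.1 (CLUE Vision Scores) says the two-week score "will be analyzed using a linear mixed model adjusting for baseline scores as a covariate". It adds that "Strata (hyperope and myope) will be included as the only fixed effect", so there is one common baseline slope and no baseline-by-stratum term. Site is random and degrees of freedom follow Kenward-Roger. Inference is on the LS mean: "Mean estimates will be conducted using two-sided confidence intervals (CI) constructed for the least square mean". The section does not give the baseline value at which that mean is evaluated.

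The parameter in each hypothesis "represents the population mean for the investigational lens after 2-weeks lens wear" in the named stratum, compared with 41 (myopes) or 36 (hyperopes). Section 14.6 analyses the secondary CLUE vision, comfort and handling scores "using the same model as described above for primary analysis of CLUE vision scores". That makes two co-primary and six secondary tests.

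Section 14.4 says "The Type I error rate of the trial will be controlled at 1-sided 0.025 level". Section 14.2 sized the CLUE endpoints within each stratum "using one-sided, one-sample mean t-test, with a one-sided Type I error rate of 0.025 for each hypothesis", with no baseline covariate. Section 14.1 leaves further detail to a stand-alone SAP, which is not among the documents available here.

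**The concern.** Baseline adjustment is routine for a difference between randomised arms. Here a single mean is compared with a constant, and two things change.

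1. **Target.** With a common slope, an LS mean taken at the pooled baseline mean is the stratum mean shifted by the slope times the distance between the pooled and the stratum baseline mean. It matches the hypothesis only if the strata share a baseline mean or the slope is zero.
2. **Standard error.** The model-based standard error treats the observed baselines as fixed. The sampling error of the baseline mean carries through to the estimate and is not counted. The Kenward-Roger method does not restore it.

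A baseline gap between strata is plausible but not shown. Section 14.2 says habitual-lens baseline scores "from 14 clinical studies were analyzed to establish thresholds reflecting the" real-world performance of these wearers, and the thresholds are lower for hyperopes in every domain: vision 36 v 41, handling 46 v 55, comfort 38 v 51. If hyperopes do score lower at baseline, their tests are too lenient; if they score higher, the myope tests are. The stated error control then depends on a gap and a correlation that the plan does not report.

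**Working it through.** **Inputs from the documents.** One-sided level 0.025 (Sections 14.2 and 14.4). Completers: 84 myopes and 56 hyperopes (Section 4.1), so the weights are 84/140 = 0.6 and 56/140 = 0.4. Table 7 vision means (SD): myopes 57.97 (20.282), hyperopes 54.32 (19.506).

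**Assumed, not in the documents.** Baseline SD 20 (the CLUE population SD in Section 2.2.1.2), baseline to follow-up correlation r from 0 to 0.7, and a myope-minus-hyperope baseline gap.

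**Reproducing the plan.** One-sample t-test power from the noncentral t gives 99.15% for myope vision at n = 29 (Table 6: 99.2%) and 99.04% for hyperope vision at n = 23 (Table 6: 99.0%). The other six CLUE rows of Table 6 also match. The sizing is correct, but for an unadjusted test.

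**Bias at the pooled baseline mean.**
- Hyperopes: + slope × 0.6 × gap. Slope 0.5 and gap 5 give 0.5 × 0.6 × 5 = +1.5 points.
- Myopes: − slope × 0.4 × gap = 0.5 × 0.4 × 5 = −1.0 point.

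Simulation agrees: with true means of 36 and 41, the LS means averaged 37.5 and 40.0.

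**Omitted variance at the stratum's own baseline mean.** Here the LS mean is essentially the raw stratum mean, with true variance SD²/n. The model reports about SD²(1 − r²)/n. The actual level is therefore about 1 − Φ(1.96 × √(1 − r²)): 3.1% at r = 0.3, 4.5% at r = 0.5 and 8.1% at r = 0.7.

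**Simulated one-sided Type I error, true means at threshold** (20,000 replicates, no site effect; nominal 2.5%):

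| Evaluation point | Gap | r | Myopes >41 | Hyperopes >36 |
|---|---|---|---|---|
| Pooled mean | 0 | 0.3 | 2.9% | 2.4% |
| Pooled mean | 0 | 0.5 | 3.8% | 3.1% |
| Pooled mean | 0 | 0.7 | 6.3% | 4.3% |
| Pooled mean | 5 | 0.3 | 1.5% | 5.4% |
| Pooled mean | 5 | 0.5 | 1.1% | 10.2% |
| Pooled mean | 5 | 0.7 | 1.0% | 22.4% |
| Own mean | 0 | 0.3 | 3.4% | 3.0% |
| Own mean | 0 | 0.5 | 4.6% | 4.2% |
| Own mean | 0 | 0.7 | 8.3% | 7.8% |
| Unadjusted t-test | 0 to 10 | 0 to 0.7 | 2.3–2.7% | 2.4–2.7% |

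**With a random site effect and Kenward-Roger** (16 sites, the maximum in Section 4.3; SD 20; intraclass correlation 0 or 0.05, assumed; ranges span both), at r = 0.3 / 0.5 / 0.6:
- Gap 5, pooled mean, hyperopes: 5.2% / 9.0–9.9% / 13.3–13.6%.
- Gap 2.5, pooled mean, hyperopes: 3.0–3.8% / 5.0–5.4% / 6.9–7.6%.
- Gap −5, pooled mean, myopes: 4.2–4.8% / 7.7–8.5% / 10.8–11.6%.
- Over all scenarios: own baseline mean with model standard error 2.0–5.6%; own mean with baseline sampling variance added 1.6–2.8%; no baseline covariate 1.7–2.9%.

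**At the planning means.** Table 7 means exceed their thresholds by 12.0 points (myope vision >46: 57.97 − 46) to 21.5 points (hyperope handling >46: 67.52 − 46). At r = 0.6, with gaps of up to 13 points in either direction, the planned model passes each of the eight tests with probability of about 99.5% or higher (lowest 99.49%).

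**The case against.** The strongest reply has four parts.

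- **The larger component depends on choices not in the text.** The pooled evaluation point is an assumption, the SAP may specify another, and no baseline means by stratum are given. The thresholds cannot simply be baseline means, since vision has two per stratum. Table 7 follow-up means differ between strata by 3.65 (vision), 3.96 (handling) and 7.02 (comfort), less than the threshold gaps in handling and comfort. This stands as a limit on the size: the 10% figure is conditional on a 5-point gap. It does not remove the variance part, which remains at every evaluation point.
- **The planning margins are wide.** This is correct, and the pass or fail decision is unlikely to change if the planning means hold. Section 14.2 notes, however, that the CLUE planning data come from the previous lens design, and error control concerns the case where the mean is near its threshold.
- **All co-primaries must pass.** With both CLUE vision nulls true, the joint pass rate was 0.04–0.5% in simulation. If only one null is true and the other endpoints pass easily, the chance of false success approaches that single test's inflated level.
- **Conditional standard errors are the ANCOVA convention.** So they are, but the hypothesis concerns a population mean, and inference on that requires the baseline sampling variance.

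**Conclusion.** The concern holds. The planned test does not assure the stated one-sided 0.025 level for the eight CLUE hypotheses. The mechanism is algebraic and certain; the size is not, because it depends on a correlation and a baseline gap that the documents do not report.

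With a correlation of 0.5, the hyperope vision test has a true level of about 9 to 10% if hyperopes are 5 points lower at baseline and pooled evaluation is used. It is about 4 to 5% at the stratum's own baseline mean without a site effect. With a reversed 5-point gap and pooled evaluation, the myope test is at about 8%. With zero correlation the level is close to nominal.

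This should be fixed before database lock. It does not undermine the trial if the planning means hold.

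**What to change.** For the threshold tests, estimate each stratum's mean from a model with stratum intercepts and random site but no baseline covariate. This targets the mean named in the hypothesis and matches the test used for sizing. Keep the baseline-adjusted model as a supportive analysis.

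Alternatively, keep the covariate, but state that each LS mean is evaluated at that stratum's own covariate means and that its variance includes covariate sampling error: add slope² × var(stratum baseline mean).

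Apply the same rule to the optional age, gender and ADD covariates in Section 14.5.1, and to the secondary CLUE tests in Section 14.6. Record the choice in the protocol or SAP before database lock.

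The cost is a few lines of SAP text, one model statement and slightly wider intervals. Unadjusted one-sample power at 84 and 56 completers is at least 99.89% for all eight tests; the lowest is hyperope vision >41. With a random site effect at an assumed intraclass correlation of 0.05 it is at least 99.6%.

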Historical data of the Test lens indicates there is a high rate ($\geq 90\%$) for both toric lens rotation $\leq 10^{\circ}$ and rotational lens stability. Assuming a correlation of 0.70 between left and right eyes, a total of 5000 replicating trials were simulated with reference rate of 90.2% for the percentage of eyes with small ($\leq 10^{\circ}$) absolute toric lens rotation (or 99% of eyes with rotational stability). Given the high event rate of the binary outcome, Y=1, each replicated sample was analyzed using a Bayesian beta-binomial model with correlated binary data (Diniz et al; 2010)¹⁴. A non-informative prior distribution, beta (0.5, 0.5) was used to model P_T (proportion of eyes with absolute toric lens rotation $\leq 10^{\circ}$ [or lens stability $\leq 5^{\circ}$] for the Test lens). For each simulated trial, the 95% central posterior credible interval (CrI) constructed for the percentage of eyes with absolute toric lens rotation $\leq 10^{\circ}$ [or lens stability $\leq 5^{\circ}$] for the Test lens was calculated. The null and alternative hypothesis for determining statistical significance in both endpoints were $P_T \leq 80\%$ and $P_T > 80\%$, respectively. With the proposed sample size, each endpoint (percentage of eyes with absolute toric lens rotation $\leq 10^{\circ}$ and lens stability $\leq 5^{\circ}$) has at least 96% power, i.e., 96% of the estimated 95% CrIs had the lower bound above 80%.

Co-Primary Safety Endpoint Sample Size Calculations:

Grade 3 or Higher Slit Lamp Findings (SLF) and Unacceptable Lens Fitting

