The null and alternative hypotheses for Grade 3 or higher SLFs of the investigational lens compared to the threshold of 5% are as follows:

$$H_o: p_T \ge 5\%$$

 $H_1: p_T < 5\%$

where p_T is the probability of a grade 3 or higher SLF across all study visits for test lens. Based on Bayesian posterior probability distribution of the proportion p_T , superiority is interpreted as 95% probability of test being statistically lower than the threshold of 5% (i.e., $p_T < 5\%$). If the upper bound of the 95% central posterior credible interval is below 5%, it will be concluded that there is 95% probability that the investigational lens is statistically significantly lower than 5% based on observed sample.

Bayesian Estimation and Statistical Evaluation of Hypothesis:

The null and alternative hypotheses for unacceptable lens fitting of the investigational lens compared to the threshold of 20% are as follows:

$$H_o: p_T \ge 20\%$$

 $H_1: p_T < 20\%$

where p_T is the probability of an unacceptable lens fitting across all study visits for test lens. Based on Bayesian posterior probability distribution of the proportion p_T , superiority is interpreted as 95% probability of test being statistically lower than the threshold of 20% (i.e., $p_T < 20\%$). If the upper bound of the 95% central posterior credible interval is below 20%, it will be concluded that there is 95% probability that the investigational lens is statistically significantly lower than 20% based on observed sample.

In the case of zero clinically significant SLF (or unacceptable lens fitting), a Bayesian hierarchical model accounting for zero-event problem will be considered¹⁶.

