In the event that all subjects' vision was optimized in 4 lenses (2 pairs) or less (i.e., zero optimization events), a Bayesian hierarchical model accounting for zero event problem will be considered¹⁶.

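### Rotational stability has no zero-failure rule: if every eye is stable, the planned logit priors give a lower bound of about 99.9%, some 1.2 to 2.5 points higher than the data support, with no effect on the 80% decision

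*Combined protocol and SAP*

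**What the plan says.** Rotational stability (movement with blink of 5° or less, at least 15 minutes after insertion at Visit 1) is a co-primary efficacy endpoint counted by eye (2.2.1.3, 2.3.1). Table 7 gives its historical rate as 100%. For power, Section 14.2 says the reference rate "was based on the worst-case scenario of 99%, given the historical results show 100"%.

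For the analysis, 14.5.1 states: "Absolute toric lens orientation and rotational stability will be analyzed separately using a Bayesian beta-binomial model". The link is then set out: "The probability p links to the regression variables through a logit transformation as follow", namely logit(p) = β0 + β1·lens, "with a non-informative prior N(0, 1000) for β_o and β_1 , and beta(0.5, 0.5) for ρ". The section goes straight on to the rule that the lower bound of the central 95% credible interval must exceed 80%.

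The power simulation in 14.2 used a different prior: "A non-informative prior distribution, beta (0.5, 0.5) was used to model P_T (proportion of eyes with absolute toric lens rotation" of 10° or less, or with stability of 5° or less).

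Provisions for no events appear elsewhere. In 14.5.2: "In the case of zero clinically significant SLF (or unacceptable lens fitting), a Bayesian hierarchical model accounting for zero-event problem will be considered". In 14.6, for lens fit success: "a Bayesian hierarchical model accounting for zero event problem will be" considered. Section 14.5.1 has no counterpart.

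**The concern.** When every eye is stable, the likelihood flattens out as the logit of p grows, so it puts no ceiling on the logit. A prior that is very wide on the logit scale then places most of the posterior at values of p that cannot be told apart from 1. In a one-lens trial β1 cannot be separated from β0. Its only effect is to double the prior variance of the logit, which pushes the bound up further.

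Stability is the only endpoint in Table 7 with a historical rate of 0% or 100% that has no such provision, which looks like an omission. What is at stake is the interval reported for a co-primary endpoint: it would claim more precision than about 140 to 155 subjects can give, and the prior behind it is not the one used to justify the sample size.

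**Working it through.** **Inputs**
- N = 140 completers, and N = 155 enrolled as a sensitivity (14.2). The endpoint is measured at Visit 1 and analysed in the ITT population on observed cases (14.5), so the true number lies nearer 155.
- Model and priors from 14.5.1. Assumptions: 1000 is a variance, and lens is coded 1. Then logit(p) ~ N(0, 2000), SD √2000 = 44.7. With the intercept only, the SD is √1000 = 31.6.
- Design prior from 14.2: beta(0.5, 0.5) on P_T. Inter-eye correlation for planning: 0.70.

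**Check against the plan's own figures.** The plan gives no zero-failure bound to reproduce. Its simulated powers were recomputed with the design prior:
- Slit-lamp findings, 1% against 5%: 87.7% (stated 89.3%).
- Absolute rotation, 90.2% against 80%: 95.9% (stated above 99%).
- Stability, 99% against 80%: about 100% (stated 96.8%).

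The slit-lamp figure agrees within two points. The two rotation entries in Table 6 look interchanged, which is a separate matter.

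**Likelihood with no failures.** Each subject contributes (1−ρ)p² + ρp, so L = [(1−ρ)p² + ρp]^N. This tends to 1 as p tends to 1, for any ρ.

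**How wide the prior is.** P(p < 0.001 or p > 0.999) = 2[1 − Φ(6.907/44.7)] ≈ 0.88. About 88% of the prior lies within 0.1 percentage points of 0 or 1.

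**Lower 2.5% posterior bound, all eyes stable** (numerical grid over logit p and ρ, with ρ ~ beta(0.5, 0.5)):

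| Prior | N = 140 | N = 155 |
|---|---|---|
| Planned, β0 + β1·lens | 99.91% | 99.92% |
| Planned, intercept only | 99.84% | 99.86% |
| beta(0.5, 0.5) on P_T, as in 14.2 | 98.66% | 98.79% |
| beta(1, 1) on P_T | 97.96% | 98.15% |

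Under the planned prior at N = 140, the 2.5% point of the logit is 6.97 and the median is about 34.

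**Data-only bounds, one-sided 0.025, N = 140**
- 140 independent units (the two eyes always agree): 0.025^(1/140) = 97.40%.
- 280 independent eyes: 0.025^(1/280) = 98.69%.

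**Excess of the planned bound**
- 99.91 − 98.69 = 1.22 points.
- 99.91 − 98.66 = 1.25 points.
- 99.91 − 97.40 = 2.51 points.

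**One unstable eye, N = 140.** The planned prior gives 98.37% and beta(0.5, 0.5) gives 97.89%. The two priors nearly agree again, so the distortion belongs mainly to the zero-failure case.

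**Chance of zero failures at correlation 0.70**, (0.3s² + 0.7s)^N:

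| True rate s | N = 140 | N = 155 |
|---|---|---|
| 99% | 0.98703^140 = 16% | 13% |
| 99.5% | 0.99351^140 = 40% | 36% |
| 99.9% | 0.99870^140 = 83% | 82% |

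**Effect on the decision.** With no failures, the posterior probability that p is 80% or less is below 10⁻¹³ under every prior tried.

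**The case against.** The strongest reply is that no trial conclusion moves. The only prespecified use of this interval is the comparison with 80%, and with zero failures every prior passes easily. That stands. A reader might infer that the co-primary result, the error rate or the power is at risk; the documents' own rule shows that none of them is.

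Three other stronger readings are tempting and also fail.
- **That the bound comes from the prior alone.** The data do rule out low p; the prior settles only where above roughly 98% the bound lands. The beta(0.5, 0.5) result depends on its prior too, as the beta(1, 1) figure shows.
- **That the interval is wrong by more than an order of magnitude.** On the unstable fraction, 0.09% against 2.60% is about 28-fold. But 2.60% is the exact bound for subjects with both eyes stable, while the endpoint counts eyes. The data-only bounds form a range, so no single correct value exists to take a ratio against. On the scale reported, the gap is a point or two.
- **That zero failures is the result the plan expects.** At the plan's own 99% rate it happens in only 13% to 16% of trials.

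Section 14.1 also leaves detail to a stand-alone SAP finalised before database lock. A rule could be placed there, but the text reviewed contains none.

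**Conclusion.** The point holds as a defect in a reported interval. If all eyes are stable, following 14.5.1 as written gives a lower bound of about 99.9% for a co-primary endpoint, where the sponsor's own design prior gives 98.7% and the data alone support 97.4% to 98.7%. The overstatement is about 1.2 to 2.5 percentage points.

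The 99.91% rests on reading 1000 as a variance and coding lens as 1. The intercept alone gives 99.84%, and reading 1000 as a standard deviation gives practically 100%, so each of these readings is tighter than the data allow. The event is foreseeable without being the base case: 16% at a true 99%, 40% at 99.5% and 83% at 99.9%, for 140 subjects and correlation 0.70.

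**What to change.** - **14.5.1.** Place beta(0.5, 0.5) directly on P_T in the same correlated-binary model, as 14.2 did, keeping the prior on ρ. Do this at least when all eyes meet the criterion. Using it throughout for the two rotation endpoints is simpler and costs little: recomputed power for absolute rotation is 95.9%, against 96.2% with the logit prior. State which option applies before database lock.
- **Lens term.** Delete β1·lens. This alone is not enough, since the bound stays at 99.84%.
- **14.5.2.** Name the same method for zero slit-lamp or unacceptable-fit events, in place of a model that is only to be considered. By symmetry the zero-event upper bound would be 1.34% at N = 140, still well below 5% and 20%. Confine it there to the zero-event case: wider use would lower the recomputed slit-lamp power from 94.5% to 87.7%, which is a separate decision.
- **14.6.** Do not carry this eye-level rule over. Lens fit success is defined per subject, and 14.2 used beta(1, 1) for it.

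The cost is a few lines of wording, one alternative program call and a slightly less favourable reported bound. With the rule limited to zero failures, the bounds still fall in the right order: 98.66% with no failures, then 98.37% with one unstable eye under the planned prior.
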